9.3.3.12 Prior and concomitant treatments

All treatments obtained before study start (initiated and stopped before study start) is defined as prior treatments. Prior treatments meeting the criteria listed below are considered to be relevant to the study indication have to be documented:

- Slow-acting drugs
 - Glucosamine
 - Chondroitin
 - Gialuronic acid
 - Diacerein
 - Unsaponifiable matters of avocado and soya
- Pain syndrome therapy
 - Analgesics
 - NSAID
- Topical pain therapy
 - Topical NSAID
- Intra-articulararticular injections
- Manual therapy
- Surgery
- Physiotherapy

Treatment of comorbid diseases (Diabetes mellitus, Hypertension, Obesity)

- Antihypertensive drugs
- Drugs for treatment of diabetes
- Anticoagulants
- Other

All treatments obtained in addition to Theraflex® for any indication (either initiated before study start or during the study) is defined concomitant treatments and has to be documented.

Information to be collected for medication includes:

- Trade name or INN
- Start date, stop date/ongoing
- Dose
- Unit
- Frequency
- Application route
- Indication

9.3.3.13 Laboratory parameters

No laboratory parameters will be collected.

9.3.3.14 End of observation

If available the primary reason for end of observation/study discontinuation should be stated:

- Regular end of observation
- Patient lost to follow up
- Consent withdrawn by patient
- Investigator decision
- (Serious) Adverse Event/Adverse Drug Reaction
- Pregnancy
- Lack of efficacy
- Patient died
- Change to another GI+Ch therapy (which therapy and reason for switch)
- Site closed
- Study terminated

9.3.3.15 Adverse events/Adverse events of special interest

(Serious) Adverse Events need to be collected as described in section 11.2. Information collected includes:

- Diagnosis of AE, or symptom (if diagnosis unknown)
- Start and stop date
- Seriousness
- Relatedness to therapy
- Action taken
- Event outcome
- Other specific treatment(s) of AE

9.4 Data sources

The investigator collects historic data (demographic and clinical characteristics) from medical records if available. Likewise, the investigator collects treatment related data during visits that take place in routine practice. Each patient is identified by a unique central patient identification code, which is only used for study purposes. For the duration of the study and afterwards, only the patient's treating physician or authorized site personnel is able to identify the patient based on the patient identification code.

9.5 Study size

The study will be analyzed descriptively. Therefore the study is not statistically powered. It is planned to enroll 1100 subjects into the study.

9.6 Data management

A Contract Research Organization (CRO) will be selected and assigned for EDC system development. The CRF will be part of the EDC system which allows documentation of all outcome variables and covariates by all participating sites in a standardized way. Information on the EDC system is available upon request (Table 3, Annex 1). Detailed information on data management, including procedures for data collection, retrieval and preparation are given in the Data Management Plan (DMP), which is available upon request (see Table 3, Annex 1).

For information on quality control, refer to section 9.8.

9.7 Data analysis

All variables will be analysed in an exploratory manner with appropriate descriptive statistical methods: categorical variables by frequency tables (absolute and relative frequencies) and continuous variables by sample statistics (i.e. mean, standard deviation, minimum, median, quartiles and maximum).

Statistical analyses will be performed using validated statistical software (e.g. SAS, SAS Institute Inc.).

All statistical details including calculated variables and proposed format and content of tables will be detailed in the statistical analysis plan (SAP). The SAP will be finalized before study database lock. The analysis will be performed in accordance with the European Network of Centres for Pharmacoepidemiology and Pharmacovigilance (ENCePP) Guide on Methodological Standards in Pharmacoepidemiology.

9.7.1 Statistical considerations

Statistical analyses will be of explorative and descriptive nature.

All variables will be analyzed descriptively with appropriate statistical methods: categorical variables by frequency tables (absolute and relative frequencies) and continuous variables by sample statistics (i.e. mean, standard deviation, minimum, median, quartiles and maximum). Continuous variables will be described by absolute value and as change from baseline per analysis time point, if applicable.

Additionally, measured HOOS/KOOS subscales values and changes from baseline will be presented using 95% CI.

All analyses will be performed for the total study population (overall analysis). Patients receiving at least one dose of Theraflex® will be included in the analysis. Whenever reasonable, data will be stratified by subgroups (e.g. age, gender, baseline characteristics).

Sample size and disposition information by analysis time point will be displayed in a frequency table.

All therapies documented will be coded using the World Health Organization – Drug Dictionary (WHO-DD). Medical history, any diseases and AEs will be coded using the latest Medical Dictionary for Regulatory Activities (MedDRA) version.

All statistical details including calculated variables and proposed format and content of tables will be detailed in the Statistical Analysis Plan (SAP). The SAP will be finalized before study database lock. The SAP is available upon request.

It is planned to have 1 interim analysis after 50% of (first 550 enrolled) subjects have completed V2. The main purpose of Interim analyses to assess the changes after the first course of treatment with Theraflex®. The final analysis will be performed after end of the study which is the date the analytical dataset is completely available.

9.8 Quality control

9.8.1 Data quality

Before study start at the sites, all investigators will be sufficiently trained on the background and objectives of the study and ethical as well as regulatory obligations. Investigators will have the chance to discuss and develop a common understanding of the study protocol and the CRF.

A CRO will be selected and assigned for EDC system development, quality control, verification of the data collection, data analysis and data transfer to Bayer.

All outcome variables and covariates will be recorded in a standardized CRF. After data entry, missing or implausible data will be queried and the data will be validated. A check for multiple documented patients will be done.

Detailed information on checks for completeness, accuracy, plausibility and validity are given in the Data Management Plan (DMP). The same plan will specify measures for handling of missing data and permissible clarifications. The DMP is available upon request (see Table 3: List of stand-alone documents, Annex 1).

Medical Review of the data will be performed according to the Medical Review Plan (MRP). The purpose of the Medical Review is to verify the data from a medical perspective for plausibility, consistency, and completeness and to identify potential issues that could affect the robustness of the collected study data or the progress of the study. Detailed information on the Medical review will be described in the MRP, which is available upon request (see Table 3, Annex 1).

National and international data protection laws as well as regulations on observational studies will be followed. Electronic records used for capturing patient documentation (eCRF) will be validated.

9.8.2 Quality review

In a subset of patients source data verification will be conducted. The purpose is to review the documented data for completeness and plausibility, adherence to the study protocol and verification with source documents.

The data quality will be assured by using by telephone interview and quality review visit:

Telephone interview

During the telephone interview the officer, responsible for the telephone interview:

- Ensures adherence to NIS protocol and any amendments

Quality review visit in the study centers

The individual, responsible for data review will have an access to the data of the patients in the centers. The quality review will consist of two parts: interview and verification of the compliance of the data presented in the Case Report Forms with the data of the primary documentation.

During conduction of the NIS the person responsible for the quality review:

- controls observance of the protocol and amendments to it;
- controls completeness and accuracy of entry of the data into CRF and their compliance with the data of the primary documentation;
- shall have an access to any documentation related to the NIS.

Detailed measures for quality reviews will be described in the Quality Review Plan (QRP). The QRP is available upon request (see Table 3, Annex 1).

9.9 Limitations of the research methods

The non-interventional study design was chosen to allow evaluation (or assessment) of current clinical practices. In contrast to clinical studies, the design of non-interventional studies (NIS) does not include randomization and "blinding", and selection of patients does not depend on the strict criteria of inclusion/exclusion. There are also limitations to this design (e.g. no possibility for comparison), but for the purpose of the objectives in this study this methodology shall provide sufficient data.

Non-interventional studies are a valuable instrument as they allow analysis samples of patients without special selection during routine clinical practice.

A prospective non-interventional study, in contrast to a retrospective one, makes it possible to plan in advance the design, procedure of gathering and processing of data, which considerably increases validity of the results.

10. Protection of human subjects

10.1 Ethical conduct of the study

This study is an observational study where Theraflex® is recommended in the customary manner in accordance with the terms of the marketing authorization. There is no assignment of a patient to a particular therapeutic strategy. The treatment recommendation falls within current practice and the recommendation of the medicines is clearly separated from the decision to include the patient in the study. The final decision on which product the patient will take is done by the patient through the purchase of the product at a pharmacy.

No additional diagnostic or monitoring process is required for participation or during the study.

Epidemiological methods will be used for the analysis of the collected data.

10.2 Regulatory authority approvals/authorizations

The study will be carried out within an approved indication and in accordance with the routine clinical practice.

Although the study is conducted in the Russian Federation, the study design is in accordance to the definition of a non-interventional study as defined in the European Clinical Trials Directive (2001/20/EC) which are further discussed in details in the "consideration on the definition of NIS trials" by the European Network of Centres for Pharmacoepidemiology and Pharmacovigilance (ENCePP, 2011).

Recommendations for NIS studies given by European Federation of Pharmaceutical Industries and Associations (EFPIA, Oct 2007) will be followed as well as ICH-GCP guidelines whenever possible.

Collection and handling of personal data in this study will be done in accordance with current local legislation (Federal Law # 152-FZ of 27.07.2006 "About personal data")

Ethical assessment will be done by expert Independent review board (IRB), specialized in NIS assessment. Protocol related documentation to be submitted to IRB for the approval, located at Inter-University Ethics Committee.

10.3 Independent ethics committee (IEC) or institutional review board (IRB)

Ethical assessment will be done by expert Independent review board (IRB), specialized in NIS assessment. Protocol related documentation to be submitted to IRB for the approval, located at Inter-University Ethics Committee:

10.4 Audit and Inspection

To ensure compliance regulatory requirements, a member of the sponsor's (or a designated CRO's) quality assurance unit may arrange to conduct an audit to assess the performance of the study at the study site and of the study documents originating from there.

The investigator/institution will be informed of the audit outcome.

In addition, inspections by regulatory health authority representatives and IEC(s)/IRB(s) are possible. The investigator should notify the sponsor immediately of any such inspection.

The investigator/institution agrees to allow the auditor or inspector direct access to all relevant documents and allocate his/her time and the time of his/her staff to the auditor/inspector to discuss findings and any issues. Audits and inspections may occur at any time during or after completion of the study.

11. Patient information and consent

Before documentation of any data, informed consent is obtained by the patient in writing. In countries where required by law or regulation, the investigator must have the IECs/IRB written approval/favorable opinion of the written informed consent form and any other written information to be provided to patients prior to the beginning of the observation.

11.1 Patient insurance

In this study, data on routine treatment of patients in daily practice are documented and analyzed with the help of epidemiological methods. Treatment including diagnosis and monitoring of therapy follows exclusively routine daily practice. Current medical daily practice is observed, and for the patient no risks beyond regular therapy exist – there is no additional hazard arising from study participation. As no study related risks exist, there is no need to protect the patient additionally by a patient insurance. The general regulations of medical law and the professional indemnity insurance of the investigators and, respectively, the institutions involved provide sufficient protection for both patient and investigator.

No study medication will be provided to participants. Thus, product insurance is covered by the existing product liability.

11.2 Confidentiality

Bayer as well as all investigators ensure adherence to applicable data privacy protection regulation. Data are transferred in encoded form only. The entire documentation made available to Bayer does not contain any data which, on its own account or in conjunction with other freely available data, can be used to re-identify natural persons. The investigators are obligated to ensure that no documents contain such data.

All records identifying the subject will be kept confidential and will not be made publicly available. Patient names will not be supplied to the MAH. If the patient name appears on any document, it must be obliterated before a copy of the document is supplied to the MAH. Study findings stored on a computer will be stored in accordance with local data protection laws.

The investigator will maintain a list to enable patients' records to be identified in case of queries. In case of a report of a serious adverse event (SAE), the responsible pharmacovigilance person may ask for additional clarification. In that case, the company is not allowed to directly contact the patient. All additional information will be provided by the investigator.

12. Management and reporting of adverse events/adverse reactions

12.1 Definitions

An adverse event (AE) is any untoward medical occurrence in a patient administered a medicinal product and which does not necessarily have a causal relationship with this treatment. An AE can therefore be any unfavorable and unintended sign (e.g. an abnormal laboratory finding), symptom, or disease temporally associated with the use of a medicinal product, whether or not considered related to this medicinal product [9].

The term also covers laboratory findings or results of other diagnostic procedures that are considered to be clinically relevant (e.g. that require unscheduled diagnostic procedures or treatments or result in withdrawal from the study). The AE may be:

- A new illness
- Worsening of a sign or symptom of the condition under treatment or of a concomitant illness
- An effect of the study medication
- An effect of the comparator product
- Off label use, occupational exposure, lack of drug effect, medication error, overdose, drug abuse, drug misuse or drug dependency itself, as well as any resulting event
- An effect related to pre-existing condition improved (unexpected therapeutic benefits are observed)
- Product exposure via mother/ father (exposure during conception, pregnancy, childbirth and breastfeeding)

As mentioned above no causal relationship with a product is implied by the use of the term "adverse event".

An Adverse Reaction (AR) is defined as a response to a medicinal product which is noxious and unintended. An AR is any AE judged as having a reasonable suspected causal relationship to Theraflex®.

Causal relationship: The assessment of the causal relationship between an AE and the administration of treatment is a clinical decision based on all available information at the time of the completion of the CRF. The assessment is based on the question whether there was a "reasonable causal relationship" to the study treatment in question. Possible answers are "yes" or "no".

An assessment of "no" would include:

The existence of a clear alternative explanation (e.g. mechanical bleeding at surgical site)

Non-plausibility (e.g. the subject is struck by an automobile when there is no indication that the product caused disorientation that may have caused the event; cancer developing a few days after the first product administration)

An assessment of "yes" indicates that there is a reasonable suspicion that the AE is associated with the use of the study treatment. Factors to be considered in assessing the relationship of the AE to study treatment include:

The temporal sequence from product administration: The event should occur after the product is given. The length of time from product exposure to event should be evaluated in the clinical context of the event.

Recovery on product discontinuation (de-challenge), recurrence on product re-introduction (re-challenge): Subject's response after de-challenge or subjects response after re-challenge should be considered in the view of the usual clinical course of the event in question.

Underlying, concomitant, intercurrent diseases: Each event should be evaluated in the context of the natural history and course of the disease being treated and any other disease the subject may have.

Concomitant medication or treatment: The other products the subject is taking or the treatment the subject receives should be examined to determine whether any of them may be suspected to cause the event in question.

The pharmacology and pharmacokinetics of the study treatment: The pharmacokinetic properties (absorption, distribution, metabolism and excretion) of the study treatment, coupled with the individual subject's pharmacodynamics should be considered.

An AE is serious (SAE) if it:

- Results in death
- Is life-threatening
- Requires inpatient hospitalization or prolongation of existing hospitalization (see exceptions below)
- Results in persistent or significant disability or incapacity
- Is a congenital anomaly or birth defect
- Is medically important.

Death is usually the outcome of an underlying clinical event that causes it. Hence, it is the cause of death that should be regarded as the SAE. The one exception to this rule is 'sudden death' where no cause has been established. In this instance, 'sudden death' should be regarded as the AE and 'fatal' as its reason for being 'serious'.

Life-threatening: The term "life-threatening" in the definition of "serious" refers to an AE in which the subject was at risk of death at the time of the event. It does not refer to an AE which hypothetically might have caused death if it were more severe.

Hospitalization: Any AE leading to hospitalization or prolongation of hospitalization will be considered as serious, unless the admission is:

- planned before subject's inclusion in the study (i.e. elective or scheduled surgery) or
- ambulant (shorter than 12 hours) or
- part of the normal treatment or monitoring of the studied disease (i.e. not due to a worsening of the disease)

However it should be noted that invasive treatment during any hospitalization may fulfill the criteria of 'medically important' and as such may be reportable as a SAE dependent on clinical judgment. In addition where local regulatory authorities specifically require a more stringent definition, the local regulation takes precedent.

Disability means a substantial disruption of a person's ability to conduct normal life's functions.

Congenital anomaly (birth defect), i.e. any congenital anomaly observed in an infant, or later in a child, should be regarded as a SAE when:

- The mother had been exposed to a medicinal product at any stage during conception or pregnancy or during delivery
- The father was exposed to a medicinal product prior to conception

Other medically important serious event: any adverse event may be considered serious because it may jeopardize the patient and may require intervention to prevent another serious condition. Medically important events either refer to or might be indicative of a serious disease state. Such reports warrant special attention because of their possible association with serious disease state and may lead to more decisive action than reports on other terms.

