12.2 Collection

Starting with the first application of Theraflex® after enrollment into the study, all non-serious adverse events (AE) must be documented on the AE Report Form or in the CRF/EDC system and forwarded to the MAH within 7 calendar days of awareness. All serious AEs (SAE) must be documented and forwarded immediately (within 24 hours of awareness). For each AE, the investigator must assess and document the seriousness, duration, relationship to product, action taken and outcome of the event.

The questionnaire related information (as it is primary and secondary endpoints) should be exempted from AE reporting.

For the reasons stated below, the following AEs are exempt from reporting in this study and will therefore not be documented in the AE Report Form in the CRF/eCRF.

- * If a pregnancy occurs during the study, although it is not a serious adverse event itself, it should be documented and forwarded to the MAH within the same time limits as a serious adverse event. The result of a pregnancy will be followed-up according to applicable Bayer SOPs. Any data on abnormal findings concerning either the mother or the baby will be collected as adverse events.
- * The documentation of any AE/SAE ends with the completion of the observation period of the patient. However, any AE/SAE - regardless of the relationship and the seriousness - occurring up to <30 days after the last dose of Theraflex® within the study period has to be documented and forwarded to the MAH within the given timelines, even if this period goes beyond the end of observation.
- * As long as the patient has not received any Theraflex® within the frame of the study AEs /SAEs do not need to be documented as such in this observational study. However, they are part of the patient's medical history.
- * For any serious product-related AE occurring after study end, the standard procedures that are in place for spontaneous reporting have to be followed.

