**IMPACT No. 19649 STATISTICAL ANALYSIS PLAN v.2.0 13 JUL 2020****10.2. Adverse events**

All AEs recorded by investigators on the Adverse event form in the CRF will be coded using the MedDRA dictionary (version 20.1 or later) according to the standard operating procedure of Data MATRIX LLC [4] and presented in separate tables by system organ class (SOC) and preferred term (PT).

Classification algorithm for AEs with missing or incomplete dates of start and end of the event is provided in section 7.2 (Table 7.2:2). If it is impossible to determine whether AE has occurred before, during, or after the study treatment, such AE will be classified as treatment-emergent AE.

Descriptive statistics for AEs will reflect the number and percentage of patients with at least one recorded AE with the relevant SOC and PT, as well as the number of these records. Patients with multiple AEs coded within the same SOC and PT will be counted only once within each SOC and PT. A patient may have multiple PTs within a SOC.

The following tables for AE data will be generated:

- Adverse events (AEs)
- AEs by intensity/severity
- AEs by relationship to the study drug
- AEs resulting in treatment discontinuation
- AEs resulting in dose reduction
- Serious AEs (SAEs)
- SAEs by intensity/severity
- SAEs by relationship to the study drug
- SAEs resulting in treatment discontinuation
- SAEs resulting in dose reduction

10.3. Only AEs classified as a treatment-emergent AEs will be included in tables. All AEs will be presented in listings. Pregnancy

No pregnancy data are collected in the study.

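### SAP 10.2 has no rule separating AE records of lack of effect, product-use departures or unexpected benefit, all of which Protocol 12.1 allows, from records of harm

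*Protocol*

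**What the plan says.** **Definition (Protocol 12.1).** The section opens with "An adverse event (AE) is any untoward medical occurrence in a patient administered a medicinal product". Its list of what an AE may be then includes "Off label use, occupational exposure, lack of drug effect, medication error, overdose, drug abuse, drug misuse or drug dependency itself". Consequences of these are listed in addition, so the word *itself* means that no medical consequence is needed. The list also includes "An effect related to pre-existing condition improved (unexpected therapeutic benefits are observed").

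**Collection (Protocol 12.2).** Once treatment is under way in the study, "all non-serious adverse events (AE) must be documented on the AE Report Form or in the CRF/EDC system", and serious events are collected on a shorter timeline. The relevant exemption is "The questionnaire related information (as it is primary and secondary endpoints) should be exempted from AE reporting".

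**End of observation (Protocol 9.3.3.14).** One primary reason is recorded. "Lack of efficacy" is one option, and an adverse event or drug reaction is a different one.

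**Tabulation (SAP 10.2, with its closing rule printed in the 10.3 heading).** All AEs on the CRF form are coded in MedDRA. The statistic is the "number and percentage of patients with at least one recorded AE with the relevant SOC and PT". Ten tables are named: AEs and SAEs, each overall, by intensity, by relationship, leading to treatment discontinuation and leading to dose reduction. Only treatment-emergent AEs enter the tables, and all AEs go to listings. No table, flag or rule refers to the type of record.

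**The concern.** The AE definition serves two purposes. For pharmacovigilance it is useful to capture lack of effect, misuse and unexpected benefit. For a safety table the reader expects untoward events. The SAP takes the pharmacovigilance set and tabulates it as if it were the second.

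AEs and SAEs are a named safety endpoint in SAP section 10. If such records are filed, a SOC percentage, a related-AE percentage or a discontinuation percentage may combine harm with treatment failure, departures in use and even benefit. The reader of the tables could not tell how much of each percentage is harm.

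**Working it through.** The documents give no AE rate, power or sample-size derivation, so there is no figure to reproduce. The check is mainly one of text.

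**1. Can such a record exist?** Yes. Protocol 12.1 allows it and 12.2 requires AEs to be documented. The questionnaire exemption removes KOOS/HOOS and satisfaction answers. It does not cover a lack of effect, or a departure in use, that the investigator separately files as an AE.

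**2. Does the treatment-emergent filter remove it?** No. The SAP's rules for classifying AEs with incomplete dates (Table 7.2:2) compare the event date with the start of the study drug. Lack of effect, a departure in use and benefit all arise on treatment, so they pass.

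**3. Does the relationship table separate it?** No. Protocol 12.1 first defines an adverse reaction as noxious and unintended, then as any AE with a reasonable suspected causal link. SAP 10.2 tabulates by relationship and applies no noxiousness criterion. A benefit record judged causal would count as drug-related.

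**4. Does the discontinuation table separate it?** No. A lack-of-effect AE recorded as leading to treatment stop enters that table. The same patient may appear in the SAP 8.1 withdrawal table under the efficacy reason. No rule reconciles the two.

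**5. Can harm be recovered from the PT rows?** Not in general. Take a SOC with two harm PTs (*a* and *b* patients), one special-situation PT (*c* patients) and a SOC count *S*. Patients may have several PTs but count once in *S*. The harm-only count *H* is then known only to satisfy

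max(*a*, *b*, *S* − *c*) ≤ *H* ≤ min(*a* + *b*, *S*).

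The PT rows show that the special-situation records exist, but they fix *H* only in special cases. The same holds for any total row, although the SAP does not name one.

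**6. Size.** The only input from the documents is the planned 1100 patients (Protocol 9.5, SAP 4.3). Each 1% with such a record and no other AE adds 1100 × 0.01 = 11 patients.

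For illustration, let *h* be the proportion with a harm AE and *s* the proportion with a special-situation record. Both are assumed. If they are independent, the combined proportion is 1 − (1 − *h*)(1 − *s*). In any case it lies between max(*h*, *s*) and *h* + *s*. With *h* = 5% (55 patients):

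- *s* = 0: 5.0%, 55 patients, no distortion.
- *s* = 1%: 1 − 0.95 × 0.99 = 5.95%, about 65 patients (bounds 5% to 6%).
- *s* = 5%: 1 − 0.95 × 0.95 = 9.75%, about 107 patients (bounds 5% to 10%).
- *s* = 10%: 1 − 0.95 × 0.90 = 14.5%, about 160 patients (bounds 10% to 15%).

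Over *h* = 2% to 10% and *s* = 1% to 20%, the combined figure under independence runs from 2.98% to 28.0%. The width of that range reflects the lack of information in the documents. It is not an estimate.

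**The case against.** The best case for leaving the SAP alone has five parts.

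- **Separability.** Percentages are given per SOC and PT, so a lack-of-effect or misuse term has its own row, and listings show every record. This stands at PT level. It does not yield a harm-only SOC, related-AE or discontinuation percentage.
- **The exemption.** The questionnaires cover pain, symptoms, function, quality of life and satisfaction, which is where lack of effect or benefit would mostly show. This stands and should reduce the number of such records. It does not remove one that has been filed.
- **Separate fields.** A reader might infer that every patient who leaves for lack of efficacy is automatically an AE case. The documents do not support that. The end-of-observation reason is a different field from the AE form, SAP 8.1 tabulates it separately, and Protocol 9.2.7.4 distinguishes ending therapy from ending documentation. Likewise, dose is routine utilization data (Protocol 9.3.3.11), and nothing turns a dosing entry into an AE. In both cases an AE must also be filed.
- **Data checks.** Investigator training and medical review are planned (Protocol 9.8.1). They may limit inconsistent filing between sites, and the documents give no evidence of such inconsistency. Neither step is described as separating record types for the tables.
- **Stakes.** The study is single-arm and descriptive, and safety is not a primary or secondary objective. This stands and limits the importance of the point.

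**Conclusion.** The point holds as a gap in SAP 10.2. Followed as written, the plan would count a treatment-emergent lack-of-effect or benefit record as an AE, and as drug-related if judged causal. That conflicts with the untoward and noxious wording of Protocol 12.1. The broad list in 12.1 is a collection rule and is not itself an error.

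Two stronger readings go too far. One is that all recorded AEs enter the tables and every AE percentage is contaminated. In fact only treatment-emergent AEs are tabulated, the SAP names no single AE percentage, and PT rows are unaffected. The other is that the distortion is large. The documents give no frequency for such records, so the effect may be zero. The one fixed quantity is 11 patients per 1% of 1100, and it assumes full planned enrolment and patients with no other AE.

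This is a cheap improvement. It is not a defect that undermines the study.

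**What to change.** Leave Protocol 12.1 unchanged for pharmacovigilance reporting. In SAP 10.2:

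1. Before database lock, prespecify a MedDRA preferred-term list for special-situation records: lack of effect, off-label use, medication error, overdose, misuse, exposure without consequence, and unexpected benefit.
2. Flag records on that list that have no associated medical event, and tabulate them in one separate table. A resulting medical event stays in the main AE tables.
3. Present the treatment-emergent AE, related-AE and discontinuation percentages with and without the flagged records.

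The cost is one agreed term list and one extra table, with the with/without percentages run from the same flag. No new data and no protocol amendment are needed. If no such record was filed, the extra table says so and the two sets of percentages agree.
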